2.3 Insulin Management System

Clinical and research components of clinical care are delineated in the table below. The information included in the "Routine Clinical Care (not on study)" column represents the routine care a patient with diabetes would undergo when starting an insulin regimen without being on a research study. The information in the "Routine Clinical Care (on study)" column represents the procedures the research participants will receive as routine clinical care while on this study and not related to the research component. The procedures in the "Study Research" column represents the investigational component of this research study being evaluated and would not be included as part of the patient's routine clinical care.

	Routine Clinical Care	Routine Clinical Care		
	(not on study)	(on study)	Study Research	
Phase 1 – Titration	 Insulin pen (or syringe and needles) Paper dosage algorithm Blood glucose meter 	 Insulin pen (Lantus (U100) Solostar Pen or Toujeo (U300) Solostar Pen (as per treating Physician)) Dosage algorithm Blood glucose meter 	 Use of MDC-T app (to support insulin dosage algorithm) 	

Table. Clinical and Research Components of Patient Visits

Maintenance Block	• Iood glucose heter	Insulin pen (Lantus (U100) Solostar Pen or Toujeo (U300) Solostar Pen (as per treating Physician))Blood glucose meter	•	Use of MDC-M app
---------------------	-------------------------	---	---	------------------

2.3.1 Phase 1 - Titration

- Lantus (U100) Solostar Pen or Toujeo (U300) Solostar Pen (as per treating physician)
- MyDoseCoach Titration App (MDC-T)
- Blood Glucose Meter (any meter allowed)

2.3.2 Phase 2 - Maintenance

- Lantus (U100) Solostar Pen or Toujeo (U300) Solostar Pen (as per treating physician)
- MDC-M app
- Blood Glucose Meter (any meter allowed)

2.4 Outcome Assessment

The MDC app will be evaluated using a combination of clinical, behavioral, psychosocial, provider, patient and process measures, in addition to MDC analytics, as described in this section.

2.4.1 Clinical Data/EMR Abstraction

Intervention Group

Phase1 (Titration) Clinical: HbA1c will serve as the primary outcome and clinical measure to determine the impact of the MDC-T app on glycemic control from baseline to 3 months. Related measures to be collected will include: Change in FBG from baseline to 3 months, rate of patients who attained individualized titration target, the time it took to attain titration target and number and type of hypoglycemic events, which are defined as follows:

- Mild/asymptomatic hypoglycemia blood glucose <70 mg/dl and no symptoms;
- Moderate/symptomatic hypoglycemia blood glucose <70 mg/dl and symptoms;
- Severe/symptomatic hypoglycemia requires assistance of another person to resuscitate because blood glucoses are too low to maintain consciousness.

Hypoglycemic data will be collected in the following ways:

1) ask the patient to contact study team if/when it happens,

- 2) ask patient at each study visit,
- 3) review of MDC information,
- 4) review of EMR,

Data will be collected on an AE form for each patient and reported if an SAE. In addition, blood pressure, cholesterol and BMI data will be retrieved from the patient's EMR record.

Phase 2 (Maintenance) Clinical: HbA1c will serve as the primary outcome to determine the longer term impact of MDC-M app on maintenance of glycemic control from 3 months to 6 months for those patients achieving glycemic targets during the MDC-T titration phase. Related measures to be collected will include the number of patients who maintained individualized glycemic targets, change in FBG from 3 months to 6 months, and record of reported hypoglycemic events (following same definitions and data collection plan as described for Phase 1). Additionally, blood pressure, cholesterol and BMI data will be retrieved from the patient's EMR record.

All of the aforementioned data will be collected for the intervention group in accordance with the study calendar in section 2.2.5.

Control Group

A majority of the data is also expected to be available within the EMR for the control group. HbA1c, FBG, blood pressure, cholesterol, and BMI data should be recorded and accessible for patients. In addition, many patients also have BG meter readings. At a minimum, we will select patients who have HbA1c values that correspond to baseline [index date = date of insulin initiation] and follow-up time points/time frames that correspond with those described in the study calendar (section 2.2.5). EMR records, including notes, downloads, and related documented data will be reviewed to identify and classify hypoglycemic events according to already aformentioned definitions.

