1.4.1 MyDoseCoach Application

MDC is an FDA-approved digital solution comprising a smartphone app for people with T2DM and web portal for healthcare professionals (HCPs). The **MDC Basal Titration Module** (MDC-T) provides a digital alternative to the manual titration model that is typically used for dose modification of longer-acting basal insulin for patients with T2DM. This allows the HCP to tailor the dosing instructions to the individual patient based on the HCP's independent professional judgment. The HCP defines an individualized longer-acting basal insulin titration plan that is used in MDC to give dose recommendations to the user based on their FBG readings and hypoglycemic event data. MDC provides similar functionality as a paper-based tool, while automatically calculating the median FBG value and instructing the patient on the next appropriate insulin dose according to a dose plan and dose adjustment rules set by their HCP.

[figure not shown]
The MDC app is also designed to support patients in maintaining proper insulin dosing to help ensure ongoing glycemic control. Like the titration module, the **MDC Maintenance Module** (MDC-M) is intended for use by HCP's and patients to enable logging of insulin and non-insulin medication use and BG measurements and provide dosing and measurement reminders.

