2.5.2 Secondary Endpoints

2.5.2.1 Phase 1 (Titration)

- Change in HbA1c from baseline to 3 months within and between groups
- Proportion of patients reaching HbA1c <7% at 3 months as compared to patients using SOC
- Change in FPG from baseline to 3 months within and between groups
- Patient-reported changes in behavioral and psychosocial outcomes from baseline to 3 months (survey)
- Patient-reported acceptability of and satisfaction with MDC-T (survey)
- Provider-reported acceptability of and satisfaction with MDC-T (survey)
- Rate of escalation to Endo (Endocrine visits) for patients using MDC-T
- Safety end points (including hypoglycemia, any untoward adverse events)
- Number and type of technical complaints

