8.2 Obligations and Responsibilities of the External Sponsor

The External Sponsor shall be responsible for transmitting to Sanofi all AE's occurring with the use of Sanofi medicinal products.

All complaints and adverse events will be managed and reported in compliance with all applicable regulations and included in the final clinical study report.

For the intervention group:

- All AEs, regardless of seriousness or relationship to Sanofi Medicinal product and study medical devices (e.g., MDC app), spanning from the signature of the informed consent form until the end of the study as defined by the protocol for that patient, are to be recorded on the corresponding page(s) or screen(s) of the CRF.
- Any defect in the device or medical device complaint, with AE must be reported within 24 hours in case of potential Adverse Event or Serious Adverse Event or without AEs must be reported within 5 days by the Investigator in order for a product technical complaint to be completed. Appropriate information (e.g., samples, labels, or documents such as pictures or photocopies) related to product identification and product deficiencies may need to be gathered. The investigator will assess whether or not the quality issue has to be reported together with an AE or SAE.
- Whenever possible, diagnosis or single syndrome should be reported instead of symptoms. The Investigator should specify the date of onset, intensity, action taken with respect to Sanofi Medicinal product or Medical Device, corrective treatment/therapy given, additional investigations performed, outcome, and his/her opinion as to whether there is a reasonable possibility that the AE was caused by Sanofi Medicinal product(s), Medical Device or by the study procedure(s).
- The Investigator should take appropriate measures to follow all AEs until clinical recovery is complete and laboratory results have returned to normal, or until progression has been stabilized, or until death, in order to ensure the safety of the patients. This may imply that observations will continue beyond the last planned visit per protocol, and that

additional investigations may be requested by the monitoring team up to as noticed by the Sponsor.

- When treatment is prematurely discontinued, the patient's observations will continue until the end of the study as defined by the protocol for that patient.
- Laboratory, vital signs abnormalities are to be recorded as AEs only if:
 - Symptomatic and/or

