 - Requiring either corrective treatment or consultation, and/or
 - Leading to Lantus (U100) or Toujeo (U300) discontinuation or modification of dosing, and/or
 - Fulfilling a seriousness criterion, and/or
 - Defined as an AESI

For the retrospective control group:

The Sponsor will transmit at the time of the analysis and at the latest the time of study report to Sanofi safety signals or conclusions with potential safety impact if any, based on data documented within the EMR.

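### Hypoglycemia is sought through four sources in the intervention group but only one in controls, so any side-by-side figures would not be like-for-like

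*Combined protocol and SAP*

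**What the plan says.** Section 2.4.1 lists "number and type of hypoglycemic events" among the Phase 1 measures and defines three classes. Mild is a glucose below 70 mg/dl without symptoms, moderate is the same with symptoms, and severe needs another person's help. For the intervention group it then gives four ways of finding events:

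- "ask the patient to contact study team if/when it happens"
- questioning at every study visit
- "review of MDC information"
- EMR review

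The app handles such data as part of its function. According to section 1.4.1 it is used to "give dose recommendations to the user based on their FBG readings and hypoglycemic event data".

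For controls, the same section gives one route: "EMR records, including notes, downloads, and related documented data will be reviewed to identify and classify hypoglycemic events", under the same definitions. It adds that many controls, not all, have meter readings.

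Section 2.5.2.1 lists as a secondary endpoint "Safety end points (including hypoglycemia, any untoward adverse events"). The line names no comparator, metric or time basis. The HbA1c and FPG lines beside it do name a comparison. Section 2.6.2 does not mention hypoglycemia.

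Safety recording in section 8.2 differs in a similar way. "All AEs, regardless of seriousness or relationship to Sanofi Medicinal product and study medical devices" go on the CRF in the intervention group. For controls, the sponsor passes on "safety signals or conclusions with potential safety impact if any, based on data documented within the EMR".

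**The concern.** Common definitions make two counts comparable only if events had a similar chance of being found. Here three of the four intervention sources have no stated counterpart in controls. A mild event is nothing more than a low reading, so it exists in the data only if a reading was logged or downloaded. A moderate event needs both a reading and a record of symptoms.

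Section 6.1 gives serious hypoglycemia after an incorrect dose recommendation as an example of the risks analysed for the app, so a reader will look to these figures when judging its safety. If all-source intervention events stood next to EMR-only control events, MDC could look less safe than it is, or a true reduction could be hidden. If controls happened to be the better documented group, an excess with MDC could be masked.

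Matching does not help. The propensity score in section 2.6.2 uses age, gender, BMI and HbA1c, and possibly race and comorbidity count. None of these describes how events were found.

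**Working it through.** **The plan's own figure.** The only sizing figure concerns HbA1c (section 2.6.1: SD 1.5, 109 per group, precision ±0.40). It reproduces: 1.96 × 1.5 × √(2/109) = 0.398. It has no bearing on hypoglycemia, for which the documents give no event rate, capture rate or margin.

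**Sources side by side (section 2.4.1).**

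| Source | Intervention | Control |
|---|---|---|
| Patient contacts study team | yes | no |
| Questioning at visits | yes | no |
| App data | yes | no |
| EMR | yes | yes, retrospective, including downloads |

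The EMR is the one shared source. Even there, the control review explicitly takes in downloads, while the intervention group's app data are listed as a source separate from the EMR.

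**Illustration with assumed capture.** Let c1 and c0 be the shares of true events found in the intervention and control groups. All values are assumptions, and the true ratio is 1.0.

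Counts: apparent rate ratio = true ratio × c1/c0.

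- 0.90/0.90 = 1.00
- 0.90/0.70 = 1.29
- 0.90/0.50 = 1.80
- reversed, 0.70/0.90 = 0.78

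Any event, with k events per affected patient and each found independently: apparent risk ratio = [1 − (1 − c1)^k] / [1 − (1 − c0)^k].

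| c1 vs c0 | k = 1 | k = 2 | k = 3 |
|---|---|---|---|
| 0.90 vs 0.50 | 1.80 | 0.990/0.750 = 1.32 | 0.999/0.875 = 1.14 |
| 0.90 vs 0.70 | 1.29 | 0.990/0.910 = 1.09 | 0.999/0.973 = 1.03 |
| 0.70 vs 0.90 | 0.78 | 0.910/0.990 = 0.92 | 0.973/0.999 = 0.97 |

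The distortion is largest for counts and for patients with a single event. It is small for an any-event outcome when events recur.

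**Severe events.** These should be the least affected, but they would be few. With 109 patients and an assumed risk of 1%, 1.09 affected patients are expected, and the chance of none is 0.99^109 = 0.33. At 3%, the figures are 3.27 and 0.97^109 = 0.04.

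**Would a plain EMR-only rule be enough?** No. It would drop the app's readings and keep control downloads. For mild events that could move the comparison towards the reversed row and under-count events with the app.

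**The case against.** The strongest reply is that the plan specifies no between-group analysis of hypoglycemia. Section 2.5.2.1 marks its comparisons, and the safety line has no such mark. Section 2.6.2 describes Phase 1 titration outcomes for the intervention group alone. Its GEE sentence concerns unnamed binary outcomes, and the binary endpoint for which a between-group comparison is named is HbA1c below 7%. Control events may be collected partly for the safety reporting in section 8.2. All of this stands. A reader might infer that the trial will formally test hypoglycemia on biased data, and the documents do not support that. Equally, they do not say that it will only be described. Control events are identified and classified within the outcome assessment section, under the same definitions, so a side-by-side table remains a natural product of the plan.

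A reader might also infer that MDC will appear to cause more hypoglycemia by some known factor. That is not supported either. Every capture value above is assumed, and section 2.2.4 chose the control clinics for the robustness of their data.

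Finally, unequal ascertainment comes with an openly declared retrospective control: past patients cannot be questioned prospectively. This is true, and it is a reason to restrict what is compared, not a reason to leave the matter open. The AE form is not in the documents, so it may already have a source field. Section 2.4.1 does not call for one.

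**Conclusion.** The asymmetry is explicit in the text. The plan does not commit to a formal comparison, but any side-by-side hypoglycemia figures drawn from it as written would not be like-for-like, mainly in the mild and moderate classes.

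Overstatement with MDC is the likelier direction, because the intervention group has three additional sources. Neither direction nor size can be derived from the documents. Under the assumed capture values the apparent ratio runs from 0.78 to 1.80 for counts, and lies closer to 1 for any-event outcomes with recurrent events. If hypoglycemia is only described within the intervention group, this bias does not arise.

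The primary HbA1c endpoint is unaffected. The point concerns what can be concluded on one secondary safety endpoint, and it justifies a cheap improvement.

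**What to change.** 1. Record the source of each intervention event (patient contact, visit question, app, EMR) when it is collected, since this may be hard to reconstruct later.
2. Report all-source intervention events descriptively, so that no harm signal is hidden.
3. State in section 2.6.2 whether hypoglycemia will be shown by group. If so, limit the display to sources available in both groups, over the same window from the index date, and say whether it shows counts or patients with any event.
4. Make clinician-documented EMR events the core comparison, with severe events shown separately.
5. Treat glucose readings alike. Either exclude control downloads together with app and meter logs, or include readings in both groups as a second, labelled analysis.
6. Keep the comparison descriptive, state the ascertainment limit, and make no claim of higher or lower hypoglycemia from all-source against EMR-only counts.

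The cost is a source field and a short paragraph. Hypoglycemic events are already listed under EMR abstraction in the study calendar (section 2.2.5). The downside is that fewer events enter the comparison and some bias remains. Study-elicited events may be charted, because the HCPs who support app use also obtain study data (section 2.2.2). Record depth may also differ between the intervention settings and the control clinics. These residual biases can act in either direction.

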2.2.5 Study Calendar

Clinical Care/EMR Data Abstraction			
Demographics ⁵	Х		
Patient History ⁶	Х		
Vital signs ⁷	Х	Х	Х
Lab work ⁸	Х	Х	Х
Self-monitoring blood glucose (SMBG)		Х	Х
Provider visits (and Endocrinology escalation visits)		х	Х
Hypoglycemic events	Х	Х	Х
Hospital stays	Х	X	Х
Adverse events	Х	X	Х

1. Education on MDC-M app only for those participants who were able to reach target FBG/A1c transition to maintenance.

2. Diabetes Medication System Rating Questionnaire-Short Form (DMSRQ-SF), Diabetes Distress Scale (DDS17) at all time points; Usability and Satisfaction surveys as 3 and 6 months.

3. Health care provider perspectives and experiences on insulin dosing survey at baseline and usability and satisfaction survey at 3 months and completion of the study.

4. Participant name, age, gender, race, ethnicity, contact information, location, marital status, employment status, education level, health insurance information

5. Diabetes duration, diabetes-related medication, diabetes-related hospitalizations, hypoglycemic events within the past year, co-morbidities

6. Blood pressure, weight, BMI

7. Fasting blood glucose, HbA1c, cholesterol, lipids (if available in clinical records); baseline values may have been collected and recorded up to nine months prior to study start (e.g., lipid panels are usually conducted once a year).

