2.6 Statistical Analysis

2.6.1 Power and Sample Size Justification

The primary objective of this study is to estimate the difference in HbA1c between the study treatment groups at 3 months. The sample size justification is based on precision estimate (i.e., confidence interval for the HbA1c difference between groups). The expected standard deviation for the 3-months change from baseline in HbA1c is 1.5. With 109 patients in the interventional arm and 109 patients in the retrospective control arm, the treatment effect, expressed as the LS means difference between arms, would be estimated with an expected precision of \pm 0.40. Additionally, this sample size allows for a sufficient number of patients after drop-out, loss to follow-up and/or missing data to enter the maintenance phase (Phase 2) of the study. Based on previous research and experiences with insulin titration, an anticipated 70% of patients (n=76) will enter Phase 2 of the study.

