2.6.2 Data Analysis

Patients will be matched 1:1 on a propensity score based on baseline demographics and clinical characteristics to improve the comparability of the interventional and retrospective groups. A logistic regression model will be used to estimate the propensity score and those baseline variables that influence treatment assignment will be included in the model. In this analysis, the following variables will be used to calculate the propensity score: age, gender, baseline BMI and baseline HbA1c. Other factors that may be included are race and number of comorbid conditions. Once the propensity score is calculated, a greedy nearest neighbor algorithm will be used for matching to form pairs of subjects from intervention and control groups with similar propensity scores. This means that for a given treated subject, the closest untreated subject within the specified caliper distance is selected for matching to the treated subject.

Descriptive statistics (e.g., demographics, duration of diabetes, etc.) will be used to describe the study groups. Baseline comparisons will be examined using standardized mean differences. A linear mixed model will be used to adjust the fixed effect of baseline FBG and the random effect of matched pairs, allowing to estimate the treatment effect with 95% CI. . Generalized estimating equations (GEE) for binary outcomes will be for binary outcomes to compare the change in slopes of outcomes of interest between the two groups and account for matched pairs . In addition, for the intervention group only, descriptive statistics will be used to summarize other data (e.g., patient and provider surveys, MDC metrics, etc.), and thematic analysis of any qualitative findings will be made.

Phase 1 (Titration): For the intervention group only, using a descriptive statistical approach, a primary assessment of titration outcomes will be built into the study at 3 months to evaluate the MDC-T app using a combination of clinical data, provider and patient feedback and process data (including patient/provider study-specific efficiency and satisfaction surveys, DE logs, validated DMSRQ-SF and MDC analytics).

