3.2.2 Usual Care Group

- Adult male and female patients 18 to 75 years old
- HbA1c > 7.5%
- Started on basal insulin in a UPMC Diabetes Outpatient facility within the past three years of study start

• Has blood glucose data available in EMR (At least two HbA1c measurements corresponding to baseline and a subsequent time point after insulin titration) FBG readings)

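### The linear treatment-effect model adjusts for baseline FBG, which eligibility does not clearly require, so the analysed set may differ from the matched set

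*Combined protocol and SAP*

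**What the plan says.** Section 2.6.2 describes one linear outcome model: "A linear mixed model will be used to adjust the fixed effect of baseline FBG and the random effect of matched pairs". Its stated purpose is a between-group estimate with a 95% interval. The section does not name the outcome. Section 2.6.1 sizes the study on the between-arm difference in 3-month HbA1c change, so this is presumably the primary model.

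Matching comes first: "Patients will be matched 1:1 on a propensity score". For the score, "the following variables will be used to calculate the propensity score: age, gender, baseline BMI and baseline HbA1c". Race and number of comorbidities are optional. FBG is not listed.

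On baseline data:

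- **Usual care, 2.4.1.** The minimum is HbA1c: "At a minimum, we will select patients who have HbA1c values that correspond to baseline [index date = date of insulin initiation", with follow-up values to correspond. The same paragraph expects FBG to be on record but does not make it a condition.
- **Usual care, 3.2.2.** Blood glucose data must be in the EMR, explained as "At least two HbA1c measurements corresponding to baseline and a subsequent time point after insulin titration". A closing parenthesis follows, then a stray mention of FBG readings with no number and no time point.
- **Intervention, 3.2.1.** The only laboratory criterion is HbA1c above 7.5%.
- **Study calendar, 2.2.5.** Laboratory work is marked at baseline, and its note reads "Fasting blood glucose, HbA1c, cholesterol, lipids (if available in clinical records", closing the parenthesis there. Self-monitored glucose is marked at months 3 and 6 but not at baseline.

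The plan states no method for missing covariates and no rule for a pair with one incomplete member. Section 2.6.1 mentions missing data only in connection with the numbers entering Phase 2.

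**The concern.** A patient can meet the eligibility criteria, be scored, be matched, and still have no baseline FBG. Mixed-model software omits a record with a missing covariate unless told otherwise. The omission would come after matching, and matching cannot screen for it because neither FBG nor its availability enters the score.

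The groups are not randomised, so matching is the main protection against confounding. If patients leave the model after matching, the estimate comes from a set whose balance nobody has checked. The two groups could also be affected differently: intervention patients come from primary care, outpatient and inpatient settings (3.1), and controls from specialty clinics chosen for the completeness of their records. A smaller analysed set would also put the stated precision at risk.

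**Working it through.** **1. Reproduce the planned precision.** Inputs from 2.6.1: 109 patients per arm, and "The expected standard deviation for the 3-months change from baseline in HbA1c is 1.5". The 95% interval is from 2.6.2.

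Half-width = 1.96 × 1.5 × √(1/n₁ + 1/n₂)

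With 109 and 109: 1.96 × 1.5 × √(2/109) = 0.398. With a t quantile on 216 degrees of freedom it is 0.4005. The stated ±0.40 is therefore the two-sided, unpaired figure with all 218 patients analysed. It makes no allowance for a missing covariate and claims no gain from pairing or from FBG.

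**2. What is required at baseline?**

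| Variable | Intervention | Usual care | Role |
|---|---|---|---|
| HbA1c | Required (3.2.1) | Required (2.4.1, 3.2.2) | In the propensity score; not in the linear model |
| FBG | No criterion | Expected (2.4.1); ambiguous and undated (3.2.2) | Covariate in the linear model; not in the propensity score |

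The value required in both groups is not the model's covariate, and the covariate is not clearly required in either group.

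**3. Effect on precision, for illustration.** The share without baseline FBG is not in the documents, so the rates below are assumptions. Only controls are taken to lack it.

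| Controls without FBG | Controls left | Partners kept (109 vs controls left) | Whole pairs discarded |
|---|---|---|---|
| 0% | 109 | 0.398 | 0.398 |
| 20% | 87 | 0.423 | 0.446 |
| 30% | 76 | 0.439 | 0.477 |
| 40% | 65 | 0.461 | 0.516 |

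For example, at 30% with partners kept: 1.96 × 1.5 × √(1/109 + 1/76) = 0.439.

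The third column is closer to the plan, because a random pair effect keeps a patient whose partner is omitted.

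**4. Allow for within-pair correlation.** A simulated mixed model (109 pairs, SD 1.5, random pair effect, no covariate, partners kept, 200 replicates per setting) gave these mean half-widths:

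| Within-pair correlation | 0% missing | 20% missing | 40% missing |
|---|---|---|---|
| 0.1 | 0.376 | 0.400 | 0.436 |
| 0.3 | 0.332 | 0.361 | 0.398 |

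Positive correlation can therefore absorb much of the loss. The documents give no correlation either.

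**The case against.** The strongest reply is that the plan does intend to have FBG. Sections 2.2.4 and 3.1 say the control clinics were chosen because their titration data are the most robust, and they name FBG. Section 2.4.1 lists FBG change among the measures to be collected in the intervention group. Section 2.5.2.1 makes 3-month change in fasting glucose a between-group secondary endpoint without qualification, whereas 2.5.2.2 attaches an availability condition only to the 6-month one. The calendar's qualifier may apply to lipids alone; if it reaches FBG, it also reaches HbA1c. The fragment in 3.2.2 may be a damaged FBG requirement. All of this stands as evidence that FBG is expected. It does not make FBG a condition of entry. HbA1c is separately required elsewhere and FBG is not. Even the favourable reading of 3.2.2 sets no baseline timing and does not bind the intervention group.

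A second reply is that baseline BMI is in the propensity score and is not an eligibility criterion either. True, but a patient without BMI cannot be scored and so drops out before pairing. A missing FBG acts after pairing.

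Third, 2.6.2 does not name the outcome, so treating this as the primary HbA1c model is an inference. That is fair, and the fix should settle it.

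A reader might go further and infer that pairs will break, that balance is lost and that ±0.40 will not be reached. The documents do not support this. They give no missingness rate, omission is a software default rather than a stated rule, and modest within-pair correlation can hold the half-width near 0.40. When only controls lack FBG, the figure of 0.48 at 30% requires discarding whole pairs, which 2.6.2 does not specify.

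**Conclusion.** The point holds as a mismatch between the model and the data the plan clearly requires. The only linear treatment-effect model depends on baseline FBG, while only HbA1c is clearly required at baseline in both groups. The analysed set may therefore differ from the matched set, and neither the matched balance nor the ±0.40 is assured.

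The size cannot be fixed from the documents. Under assumed control losses of 20, 30 and 40%, the half-width rises from 0.40 to about 0.42, 0.44 and 0.46 by the unpaired formula, and to less than that if within-pair correlation is positive. The effect on precision is modest. In a non-randomised comparison, the possible loss of matched balance matters more. The conclusion assumes that the model in 2.6.2 serves the primary endpoint and that default handling of missing covariates applies.

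This is more than an omitted detail, because the choice of covariate itself opens the gap and a covariate required in both groups is at hand.

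**What to change.** In 2.6.2:

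- State that the primary model is for 3-month change in HbA1c, adjusted for baseline HbA1c with the random effect of matched pair. Baseline HbA1c is required in both groups, so no matched patient is lost through a missing covariate, and 109 against 109 keeps the half-width at 0.398. Missing 3-month outcomes are a separate matter.
- Keep the FBG-adjusted model as a sensitivity analysis. Say in advance whether missing baseline FBG is imputed or the analysis is restricted to patients with a recorded value.

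In 3.2.2 and 2.4.1, reconcile the FBG wording: say whether an FBG value is required of controls and, if so, at what time.

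The cost is a change of wording, with no new data. The primary model gives up any variance reduction, or adjustment for imbalance, that is specific to FBG. The documents do not quantify either, the stated precision does not rely on the first, and the sensitivity analysis covers both.

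If the sponsor prefers FBG in the primary model, a recorded baseline value should be required in both groups before matching, or an imputation method pre-specified. The first route shrinks the control pool and moves the same selection ahead of matching. Simply recruiting more is expensive: if 20% in each arm lacked FBG, keeping 109 analysable would take 109/0.8, or 137, per arm.
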